Aim 3: Evaluate facilitators of and barriers to scalability, acceptability, and sustainability of financial incentives plus tailored messages based on SDT principles, financial incentives, and tailored messages based on SDT principles. To identify facilitators of and barriers to intervention implementation and sustainability, we will interview participants, workplace health promotion staff, and health system staff. With these interview data and program cost data, we will evaluate program implementation and sustainability using an integration of the Reach, Effectiveness, Adoption, Implementation, and Maintenance and Consolidated Framework for Implementation Research frameworks.

Aim 4: Compare 12-month changes in HbA1c and weight in the Enhanced Usual Care (EUC) arm to similar patients who received no intervention. This exploratory aim was added after analyses of primary and secondary outcomes found that participants in the least research-intensive arm, the Enhanced Usual Care (EUC) arm, saw the best improvements in weight and HbA1c. We will conduct an analysis to compare the HbA1c and weight outcomes in the EUC arm to similar patients who received no intervention (external controls). The results will be used to provide context to staff who we interview as part of Aim 3.

Background Information

Significance

Prediabetes Is a Major Public Health Problem in the United States. Prediabetes is an asymptomatic condition in which patients' blood glucose levels are higher than normal but not high enough to meet diagnostic criteria for type 2 diabetes mellitus (T2DM). The American Diabetes Association (ADA) defines prediabetes as either a fasting plasma glucose (FPG) of 100 to 125 mg/dL, a 2-hour plasma glucose of 149 to 199 mg/dL after a 75-gram oral glucose tolerance test, or a hemoglobin A1c (HbA1c) of 5.7% to 6.4%. An estimated 84 million US adults have prediabetes, which is associated with an approximately 3-fold greater annual incidence of T2DM and an approximately 50% greater risk of consequent cardiovascular disease.

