We will then, in an equal ratio, randomly allocate participants to an: (1) Enhanced Control Arm, (2) Financial Incentives Arm, (3) Tailored Messages Arm, or (4) Combo Arm.

Prior to start of recruitment, the W2H platform will be programmed to randomize with variable block lengths (block lengths: n=1, n=2) and stratification by participants' household income and autonomous motivation to prevent diabetes. Data on household income and autonomous motivation to prevent diabetes will be collected from the baseline survey. For household income, three levels of stratification will be used to ensure a balance of lower-income households among the arms: below \$45,000, \$45,000 and above, and non-response. Stratification on the sum score for autonomous motivation to prevent diabetes -- derived from the Treatment Self-Regulation Questionnaire administered in the baseline survey -- will use two levels: less than 35 to indicate lower autonomous motivation and 35 or higher to indicate higher autonomous motivation.

The allocation sequence will be generated dynamically by the randomization program so that research staff will not be able to predict future assignments.

Arm assignments will be communicated to participants by an email and text message. Neither participants nor the Research Coordinator will be blinded to arm assignment due to the nature of the interventions. All investigators, data analysts, and the project manager will be blinded to arm assignment until primary outcome data are collected.

Interventions

Enhanced Control Arm [ECA]. Starting on the first day of the intervention, participants will all receive a series of initial educational messages delivered via text message. These messages will welcome participants to the study, set expectations for the following 12 months, and establish a consistent minimum level of knowledge among all participants on the topics of prediabetes, the DPP, and metformin. Participants will receive one of these messages each day for the first two weeks of the intervention.

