Our primary analytic approach will use ordinary least squares (OLS) regression models for continuous outcomes, adjusting for two stratification variables used in randomization (household income and autonomous motivation to prevent diabetes). To assess balance in randomization, we will compare baseline survey measures across arms. Additionally, we expect some missing data on baseline measures and outcomes and will assess the extent and pattern of missingness (e.g., monotone missingness) and predictors of missing outcomes. If we find a baseline measure to be predictive of missing outcome data, we will also adjust for this measure in analyses of outcomes. As an alternative analytic strategy, we will also use mixed-effects models. We will assess for consistency in the results between the two analytic approaches. If more than 10% of the 12-month data are missing, we will also use a multiple imputation strategy in which we will generate ten imputed datasets for missing data using a sequential regression multivariable imputation method, including intervention arms and other baseline variables.¹⁸⁵ The estimates from both the OLS and mixed-effects model analyses using imputed datasets will then be combined using the method of Rubin and Little.¹⁸⁶ All analyses of outcomes will use an intent-to-treat approach and a Bonferroni corrected α of 0.017. Data will be analyzed by a Data Analyst who will be blinded to arm assignment until all primary outcome data have been collected.

Aim 1: Compare the effectiveness of financial incentives plus tailored messages based on SDT principles, financial incentives, and tailored messages based on SDT principles in decreasing hemoglobin A1c, and weight, and in increasing participation in a DPP or use of metformin.

H1a: The mean decrease in HbA1c will be greater in the Combo Arm than in the Enhanced Control Arm.

H1b: The mean decrease in HbA1c will be greater in the Combo Arm than in the Financial Incentives Arm and the Tailored Messages Arm.

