Mean 12-month change in HbA1c (defined as the 12-month measure minus the baseline measure) will be reported by arm. To test H1a and H1b, we will use an OLS regression model with 12-month change in HbA1c as the response variable. This model will include an indicator for each of the three arms (with the Financial Incentives Plus Tailored Messages Arm as the reference), stratification factors, baseline HbA1c values, and any baseline measures that are predictive of missing 12-month data. We will use similar, separate OLS regression models to predict our secondary outcomes of 12-month changes in weight (defined as the difference between the 12-month and baseline measures) and mean number of months (calculated out of 12 months to account for those who drop out before 12 months) in which individuals were engaged in a DPP, mean months in which individuals had a metformin PDC of at least 0.8, and mean months in which individuals were engaged in a DPP or had a metformin PDC of at least 0.8.

In alternate analyses, we will fit separate mixed-effects models for the primary and secondary outcomes using baseline, 6, and 12-month data as response variables and with time, study arm indicators, and interactions between time and study arm indicators as predictors and participants as random intercepts. We expect the changes in outcomes in intervention arms to be gradual over time and anticipate these longitudinal data models will confirm findings from our primary analytic approach to testing H1a and H1b, but if the findings differ, we will examine the source of any differences. For models for months of engagement in a DPP or use of metformin, we will first assess the distribution for skewness and, if more appropriate, a count data model (e.g., zero-inflated negative binomial) will be used instead of OLS.

Aim 2: Identify mediators and moderators of the effectiveness of financial incentives plus tailored messages based on SDT principles, financial incentives, and tailored messages based on SDT principles.

H2a: Combo Arm on 12-month change in HbA1c will be mediated by changes in autonomous motivation and changes in controlled motivation.

H2b: Effects of the Financial Incentives Arm on 12-month change in HbA1c will be mediated by changes in controlled motivation.

H2c: Effects of the Tailored Messages Arm on 12-month change in HbA1c will be mediated by changes in autonomous motivation.

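### Do block lengths given as n=1 and n=2, with no unit, undermine the balance of the four arms?

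*Combined protocol and SAP*

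**What the plan says.** Protocol, Randomization: "We will then, in an equal ratio, randomly allocate participants to an" one of four arms. Before recruitment the platform is "programmed to randomize with variable block lengths (block lengths: n=1, n=2"), stratified on two baseline survey items. For income, "three levels of stratification will be used to ensure a balance of lower-income households among the arms": below $45,000, $45,000 or more, and non-response. The motivation score "will use two levels: less than 35 to indicate lower autonomous motivation and 35 or higher to indicate higher autonomous motivation". That makes 3 × 2 = 6 strata. The section adds that the sequence is generated dynamically, which it offers as the reason staff cannot predict assignments. It describes no minimization or other balancing rule. Block length appears nowhere else in the document.

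Analysis Plans: the primary OLS approach is described as "adjusting for two stratification variables used in randomization". Under Aim 1, the HbA1c model contains the arm indicators plus "stratification factors, baseline HbA1c values, and any baseline measures that are predictive of missing 12-month data". The same section plans a comparison of the arms on baseline survey items as a check on the randomization.

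Specific Aims, Aim 4: "This exploratory aim was added after analyses of primary and secondary outcomes", so allocation and the main analyses are already done.

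**The concern.** A permuted block that balances four arms in a 1:1:1:1 ratio must hold a multiple of four participants. Block length ordinarily counts participants. Read that way, a block of one is simple randomization and a block of two reaches at most two of the four arms. No completed block could be balanced, and stratifying would restrict almost nothing. The stated purpose of the income levels would then have no mechanism behind it. At stake would be unequal arm sizes, some loss of power for the Combo Arm comparisons, and uneven low-income counts in a trial that also tests income as a moderator (H2d).

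**Working it through.** **1. The plan's own sample size.** Inputs from Sample Size: difference 0.2 (H1b) and 0.4 (H1a), SD 0.4, α = 0.017 (taken as two-sided), 85 per arm, 10% attrition, 380 enrolled.

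- n per arm = 2(z₀.₉₉₁₅ + z₀.₈₀)²(SD/δ)² = 2(2.387 + 0.842)²(0.4/0.2)² ≈ 83.4, so 84.
- Power at 85 per arm, δ = 0.2: Φ(0.2/(0.4√(2/85)) − 2.387) = Φ(0.873) = 80.9%; with the t distribution on 168 df, 80.1%. For δ = 0.4 it exceeds 99.9%.
- 340/0.90 = 378, against 380 stated (95 per arm).

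The stated figures reproduce.

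**2. Spread of arm sizes if n counts participants.** Assume blocks of 1 and 2 are equally likely and a block of 2 holds two different arms; the document states neither. The count of a given arm has variance (1/4)(3/4) = 3/16 in a block of 1 and (1/2)(1/2) = 1/4 in a block of 2. The average is 7/32 per block of 1.5 participants on average, or 7/48 per participant. Simple randomization gives 3/16 = 9/48.

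- Ratio of SDs: √(7/9) = 0.88, so this scheme is close to simple randomization.
- N = 380: SD of an arm size = √(380 × 7/48) = 7.4 (simulated 7.41).
- 76 low-income participants: √(76 × 7/48) = 3.33 (simulated 3.33).

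**3. Spread if n counts participants per arm (blocks of 4 and 8).** Only the last, incomplete block in a stratum can be unbalanced, by at most 2 between any two arms. Low-income households fall in two strata, so their largest possible gap is 2 × 2 = 4.

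**4. Simulation.** 3,000 trials per setting, N = 380, six strata. Assumed, because the document does not give them for this trial: low-income share 10/20/30%, income non-response 10%, and 60% scoring 35 or higher. Gaps are largest minus smallest arm.

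| | Blocks of 1, 2 participants | Blocks of 4, 8 | Simple |
|---|---|---|---|
| Mean whole-trial gap | 17.5 / 17.8 / 17.6 | 2.8 | 20.1 |
| Mean low-income gap | 5.6 / 7.9 / 9.6 | 1.5 | 6.4 / 8.9 / 11.0 |
| Mean H1b power (t) | 79.9 / 79.8 / 79.8% | 80.1% | – |
| 5th percentile of H1b power | 76% | 79.6% | – |

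A separate run of 4,000 trials per setting gave the chance of a low-income gap of 10 or more as about 7% / 30% / 49% with blocks of 1 and 2 participants, and 0% with blocks of 4 and 8. Its mean H1b power by the normal formula was 80.9%, against 81.1% for equal arms.

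The 60% figure matters little. In step 2 the spread depends on the number of participants, not on how they split by motivation. In step 3 it depends on the number of strata. The pilot in Preliminary Studies had 8 of 31 intervention participants below 35, which puts 23/31 = 74% at 35 or higher.

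**5. What the unfavorable reading costs.** Put the whole 95th-percentile gap of 31 between the two arms being compared, keeping their total at 190: 79.5 and 110.5 randomized, or 71.55 and 99.45 after 10% attrition. Power = Φ(0.5/√(1/71.55 + 1/99.45) − 2.387) = Φ(0.839) = 79.9%, against Φ(0.883) = 81.1% at 85.5 each. The loss is about 1.2 points. The lower 5th percentiles in step 4 arise when both compared arms happen to be small.

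For a low-income contrast between two arms, the mean standard-error factors are 0.478 against 0.465, 0.331 against 0.326, and 0.269 against 0.265. The ratios are 1.028, 1.015 and 1.015.

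**The case for a change.** The strongest case for acting is that block size is basic to any description of an allocation, and this one cannot be reproduced from the text. The dynamic generation does not fill the gap, because it is offered only to explain unpredictability. Covariate adjustment protects the estimate but does not make the statement about low-income balance true. Because H2d tests income as a moderator, readers have a direct interest in arm counts by income. Naming the unit would cost almost nothing.

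The missing unit stands: the document never supplies it. The rest is conditional. A block of one participant is not a block in any useful sense, and it would defeat the equal ratio, the varying lengths and the stratification described beside it. Read per arm, the whole paragraph is consistent and the stated lengths are unlabelled, not wrong. On the other reading balance is not enforced, but expected arm sizes remain 1:1:1:1 and reasonable balance can still arise by chance. Income and motivation are both collected in the baseline survey, so the planned comparison of arms would already show an uneven split on either.

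**Conclusion.** No change to the plan follows. The unit of n is missing, and anyone with the platform configuration can supply it when the allocation is reported. The document does not show that the allocation was faulty, and the reading that fits the rest of the paragraph (blocks of 4 and 8 participants) delivers the intended balance, with a low-income gap of at most 4.

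On the unfavorable reading the gaps would be real: a mean of about 18 across the whole trial, and 5.6 to 9.6 among low-income participants. Yet randomization stays valid, the stratification variables are in the primary model, mean H1b power falls by 0.2 to 0.3 points, H1a power at the planned 85 per arm exceeds 99.9%, and low-income contrasts lose about 1.5% to 3% in precision. Allocation is finished, and the planned analysis would be the same on either reading.

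The gap figures rest on an assumed low-income share of 10% to 30% and on the assumed make-up of a two-participant block. The conclusion does not depend on the exact values, because the effect on power and precision is small across that range.

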Ever diagnosed with T2DM as indicated by the following ICD codes: 
 • E08 Diabetes mellitus due to underlying condition • E09 Drug or chemical induced diabetes mellitus • E10 Type 1 diabetes mellitus • E11 Type 2 diabetes mellitus • E13 Other specified diabetes mellitus • 250 Diabetes mellitus (ICD-9) 	Custom Pull from MM medical records, DOCT-R and confirmed in screener questionnaire
Serious mental health conditions as indicated by the following ICD-10 codes: 
 F20 Schizophrenia F21 Schizotypal disorder F22 Delusional disorders F24 Shared psychotic disorder F25 Schizoaffective disorders F28 Other psychotic disorder not due to a substance or known physiological condition F29 Unspecified psychosis not due to a substance or known physiological condition F31 Bipolar disorder F33.2 Major depressive disorder, recurrent severe without psychotic features 	Custom Pull from MM medical records, DOCT-R

F33.3 Major depressive disorder, recurrent, severe with psychotic symptoms	

End-stage renal disease is indicated by the following ICD codes:
 
N18.6 End stage renal disease Z99.2 Dependence on renal dialysis ICD-9-CM 585.6 End stage renal disease ICD-9-CM V45.11 Renal dialysis status
	Custom Pull from MM medical records, DOCT-R
Alcohol dependence (ICD-10: F10.2) and opioid dependence (ICD-10: F11.2)	Custom Pull from MM medical records, DOCT-R
Unable to send and receive several text messages weekly	Online screener questionnaire in Way to Health (W2H) or screened over the phone by study staff; entered into Qualtrics
Does not have a smart phone	
Currently taking metformin	
Unable to take metformin due to contraindications or side effects	
Participated in a Diabetes Prevention Program covered by UM Premier Care insurance	
Currently enrolled in an interventional research study that is examining how a diet, program, or drug might: promote physical exercise, healthy eating habits, or weight loss; lower blood pressure; or lower blood sugar	
Not planning to live in local area over the next year	
Pregnant or planning a pregnancy in the next year	
Received treatment for an eating disorder (e.g. anorexia or bulimia), not including binge-eating disorder, in last 12 months	
Intensive cancer treatment such as bone marrow transplant, chemotherapy, radiation, or cancer related surgery (not including hormonal chemotherapy like Tamoxifen) in last six months or near future	

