Data pull and outreach. We will use queries of the Michigan Medicine electronic health record (EHR) to identify patients who meet the inclusion a subset of the criteria in Table 1. The A1c must have been completed at least 30 days ago and less than 12 months ago and have a value from 5.7% to 6.4%, inclusive, or not have had an A1c test in the last year. The list of patients will be reviewed to remove any patients who are not eligible because they participated in the pretesting of study intervention materials (10-30 patients). The remaining patients will be mailed (and/or emailed, when email is listed in health record) a two-sided 5x8 card, in a brightly colored envelope, that describes the study. To protect privacy, the envelope will have the University of Michigan Medical School name, return address, and the block "M," and in the bottom left corner, the text, "Chance to participate in a research study that could benefit you and your health!" On the recruitment card and email, recipients are given the chance to "opt-out" of any further communications about the study by emailing or calling the provided contact information. The email message will contain similar text and photographs as the mailed card, but exact layout will be modified to fit the communication mode.

Website on Qualtrics. The postcard and email direct them to a website hosted in Qualtrics that first asks if they received a mailed card or email about the study that was addressed to them. We ask this question because we anticipate some interested potential participants going to the website after hearing about the study from family and friends who we contact directly.

If they respond that they *did* receive a postcard or email addressed to them, they are taken to pages with more information about the study, contact information for study staff so potential participants can ask questions, and a question about their interest that, if answered affirmatively, takes them to the W2H platform so that they can begin the screening process.

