meaning. Good illustrative statements will be captured verbatim and indicated as such. Notes will be stored in a secure study folder on a departmental shared drive. Interview notes will be coded and analyzed using NVivo software. A code book will be developed beginning with the key domains from the interview guide and using an iterative process among three study staff and PI, with additional codes and subcodes added to account for details that emerged during interviews. The same four individuals will independently code four set of notes and will discuss concordance (Hemmler et al., 2022) to resolve discrepancies in coding via a consensus process. If the study team determines that a high level of consistency in coding had been established, then the sets of notes will be coded independently, with coders applying a “flag for review” code to any sections of text where the coder would like confirmation of a code via team review. If consistency in coding is not established after the group codes four sets of notes, more notes will be coded until consistency in coding is established. The codebook will be revised as needed to reflect new codes that emerge, with notes being recoded as needed. Once coding is complete, the four study team members will independently review key code reports and discuss interpretation of findings. Findings may be used to assist in interpreting study outcomes, improve the program itself, and to identify potential facilitators of and barriers to adoption, implementation, and sustainability. In reports and manuscripts, all data will be deidentified.

9. External controls data. Prior to conducting interviews with the key stakeholders described above as data source #7, we will obtain data that will allow us to share with those interviewed a comparison, between the EUC arm and similar patients who had no intervention, of changes in weight and HbA1c over approximately twelve months. Data will be of patients matching the same initial eligibility criteria that were used for the data pulls for recruitment. Patients will be excluded if they participated in the study, declined to participate after a recruitment call, were unable to reach for recruitment, or were ineligible as determined by screening. Variables provided will be: coded identifier, height, age, sex, race, ethnicity, and both weight and HbA1c with corresponding measurement dates.

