
that will be adjusted to current dollars using medical and pharmaceutical components of the Consumer Price Index. Our cost analysis will also estimate the costs of delivering each study arm, including costs associated with financial incentives and use of the W2H platform.

Sensitivity analyses will be used to examine the impact of using different cost estimates. We will provide stakeholders from Michigan Medicine, BCN, and U-M MHealthy with estimates of the costs of sustaining each approach.

Later in the study, we will develop a detailed plan to evaluate the domains of RE-AIM. Once the plan is developed, we will submit an amendment to IRB for approval.

Aim 4: Compare 12-month changes in HbA1c and weight in the Enhanced Usual Care (EUC) arm to similar patients who received no intervention. Patients receiving no intervention (external controls) will be matched or adjusted for the following characteristics: age, sex, race, ethnicity, and baseline values of BMI, weight and HbA1c. We will use an OLS regression model with 12-month change in HbA1c as the response variable. This model will include an indicator for the EUC (reference is external control), stratification factors, baseline HbA1c values, number of months between two measurements, and any baseline measures that are predictive of missing 12-month data. We will use similar, separate OLS regression models to compare 12-month changes in weight.

Privacy and Confidentiality Measures

Privacy: A potential risk of participation is a breach of a participant's privacy, in which their participation in the research is disclosed to an individual or entity the participant did not wish to have this knowledge. This risk is less serious and lessened in likelihood by collection of informed consent and survey data through the secure W2H web platform.

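### Aim 4's external controls may include baseline metformin users and prior DPP participants, whom the EUC screener excluded, and the planned data cannot identify them

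*Combined protocol and SAP*

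**What the plan says.** Measures and Data Collection, item 9 (External controls data), defines the controls by the recruitment query: "Data will be of patients matching the same initial eligibility criteria that were used for the data pulls for recruitment". Under Recruitment, the paragraph on the data pull says that EHR queries are used to "identify patients who meet the inclusion a subset of the criteria in Table 1".

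Table 1 (Inclusion and Exclusion Criteria) gives sources for the criteria. Diagnoses such as diabetes, serious mental illness and end-stage renal disease are attributed to a custom pull from the medical record. The row on text messaging is attributed to "Online screener questionnaire in Way to Health (W2H) or screened over the phone by study staff; entered into Qualtrics". The rows beneath it, among them "Currently taking metformin" and "Participated in a Diabetes Prevention Program covered by UM Premier Care insurance", show no source of their own in the text available to us.

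Item 9 then drops people who joined the trial, declined after a call, could not be reached, or were screened and found ineligible. For those left, it states: "Variables provided will be: coded identifier, height, age, sex, race, ethnicity, and both weight and HbA1c with corresponding measurement dates". Under Analysis Plans, Aim 4, the controls "will be matched or adjusted for the following characteristics: age, sex, race, ethnicity, and baseline values of BMI, weight and HbA1c". The regression is specified as follows: "This model will include an indicator for the EUC (reference is external control), stratification factors, baseline HbA1c values, number of months between two measurements", plus any baseline measure that predicts missing 12-month data.

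The Privacy and Confidentiality section limits the metformin claims feed and the Omada feed to trial participants. It also says that linked phone-screener answers are not kept for people who did not consent.

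**The concern.** The EUC arm and its comparator appear to be selected by different rules on the two treatments that the trial promotes. An EUC member had to report not taking metformin and not having used a plan-covered DPP. An external control had to meet only the query criteria. If the query did not cover these two items, some controls were already on metformin or had been through a DPP at baseline, and nothing in the planned dataset would reveal which.

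The protocol's conceptual model treats DPP participation and metformin as the drivers of HbA1c and weight, so baseline status on them bears directly on whether the controls are similar patients. Aim 4 was added because EUC unexpectedly showed the best improvements, and its result is to be given to interviewed staff as context. At stake is how far that context can be trusted.

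**Working it through.** **1. Does the gap follow from the text?**

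- Control selection: data-pull criteria only (item 9), which are part of Table 1 (Recruitment).
- The two exclusions: they sit in a run of rows that begins with the screener source. The same run includes smartphone ownership and plans to live locally, which a record query could not reliably supply. This supports reading the screener as the source for the whole run.
- Item 9's removal of people found ineligible reaches only those who were screened. With participants, decliners and unreached patients also removed, the remaining pool is mostly unscreened. A few who screened eligible but did not enrol may remain.
- Supplied variables, matching list and model: no metformin or DPP item. The clause on predictors of missingness cannot add a variable that was never obtained.
- Data already held: the claims and Omada feeds cover participants only, so they cannot fill the gap.

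**2. The plan's own figures.** Aim 4 has no stated sample size or power. The inputs borrowed below (SD 0.4, 85 per arm, α 0.017) come from Sample Size and reproduce the stated 80% power for H1b. The SE is 0.4 × √(2/85) = 0.0614, and 0.2/0.0614 = 3.26. Against a two-sided critical value of 2.387, power is 0.809 (0.801 with the t distribution).

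**3. Share of controls affected.** The Significance section reports that 8% used a DPP and 8% took metformin in one year. With full overlap, 8% had either; with none, 16%.

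**4. Shift in the control mean** = share × difference in 12-month HbA1c change between users and non-users. The difference is assumed to be 0.1 to 0.2 points.

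- 0.08 × 0.1 = 0.008
- 0.08 × 0.2 = 0.16 × 0.1 = 0.016
- 0.16 × 0.2 = 0.032

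**5. Against the SE of the EUC-control difference.** The control-to-EUC ratio is not given, so one and five controls per EUC member are assumed.

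- 1:1: 0.4 × √(1/85 + 1/85) = 0.0614
- 5:1: 0.4 × √(1/85 + 1/425) = 0.0475

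| Shift | In SEs, 1:1 | In SEs, 5:1 | Two-sided false-positive rate at α 0.017 (1:1; 5:1) |
|---|---|---|---|
| 0.008 | 0.13 | 0.17 | 1.8%; 1.9% |
| 0.016 | 0.26 | 0.34 | 2.1%; 2.3% |
| 0.032 | 0.52 | 0.67 | 3.3%; 4.4% |

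**6. What remains if only metformin users are excluded.** With no overlap, the DPP share becomes 0.08/0.92 = 8.7%, and the shift is at most 0.087 × 0.2 = 0.017. With full overlap, it is zero.

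**The case against.** The strongest reply is that the central fact is inferred. The recruitment section does not say which criteria the query covered, and blank cells in an extracted table are not evidence in themselves. Nor do blanks in this table always take the source above them: the primary-care-provider row is blank, and its apparent source follows on the BMI row. This stands, and it is why the point is conditional on what the query did.

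A reader might infer from item 9's variable list that no metformin filter was applied. The list does not show that. It also omits insurance and the diagnosis codes, which Table 1 attributes to the custom pull, so it describes what is delivered and not what is filtered. It does show that adjustment is impossible.

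The size rests on stacked assumptions, and this also stands. The 8% figures are past-year use among employees in one plan. They are not current use at a baseline date or lifetime DPP participation, and the eligible population includes dependents and two other plans. The 4.4% rate needs no overlap, a 0.2 point difference that the documents do not give, and five controls per EUC member.

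Finally, metformin and DPP are not the only screener items. Recent bariatric surgery, pregnancy and intensive cancer treatment sit in the same run of rows and could also affect weight or HbA1c. That widens the gap; it does not answer it.

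**Conclusion.** The concern holds in conditional form. Unless the recruitment query already excluded them, the Aim 4 controls may include baseline metformin users and prior DPP participants, and the plan has no means of finding or adjusting for them. Under the assumptions shown, the control mean shifts by 0.008 to 0.032 HbA1c points, or 0.13 to 0.67 of the SE of the difference. That is a modest bias.

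Three stronger conclusions are tempting but unsupported:

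- **That the bias flatters EUC, or hides its benefit.** The direction is unknown: recent starters may still be improving, while established users may be stable.
- **That any metformin or DPP use among controls is contamination.** Use begun after baseline is ordinary care; only baseline status differs by design.
- **That the trial's main findings are affected.** Aim 4 is labelled exploratory, and no randomised comparison uses these controls.

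This is a worthwhile, low-cost improvement and not a flaw in the primary analysis.

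**What to change.** First establish whether the recruitment query excluded metformin users, and state the answer in item 9. If it did not:

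- Amend item 9 to obtain dated EHR metformin prescriptions. Exclude controls with an active prescription on the date of the HbA1c used as their baseline; the protocol does not define an index date, so this definition is proposed here. It approximates the self-reported exclusion applied to EUC but is not identical to it.
- Exclude prior DPP participants if the data can be obtained. If not, report how the Aim 4 estimate moves if about 8% to 9% of controls had prior DPP.
- In the same query, apply other screener-only exclusions that the record can identify, such as recent bariatric surgery, pregnancy and intensive cancer treatment.
- State that the remaining screener criteria, and the fact that EUC members are volunteers who completed enrolment, still separate the groups.

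The cost is an IRB amendment and a few more fields in a query that item 9 describes as still to be run. Prescription orders are not fills, so some misclassification remains, and DPP history may be unobtainable for non-participants. Precision barely suffers from the metformin and DPP exclusions. Losing 8% or 16% of controls raises the SE of the difference from 0.0475 to 0.0479 or 0.0483 at 5:1 (391 or 357 controls), and from 0.0614 to 0.0627 or 0.0642 at 1:1 (78.2 or 71.4 controls).
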